**Table 2**

Proposed criteria for measurement of treatment response in adult MDS/MPN

CR (presence of all of the following improvements)*
Bone marrow: $\leq 5\%$ myeloblasts (including monocytic blast equivalent in case of CMML) with normal maturation of all cell lines and return to normal cellularity*
Osteomyelofibrosis absent or equal to “mild reticulin fibrosis” ( $\leq$ grade 1 fibrosis)‡
Peripheral blood‡
WBC $\leq 10 \times 10^9$ cells/L
Hgb $\geq 11$ g/dL
Platelets $\geq 100 \times 10^9/L$ ; $\leq 450 \times 10^9/L$
Neutrophils $\geq 1.0 \times 10^9/L$
Blasts 0%
Neutrophil precursors reduced to $\leq 2\%$
Monocytes $\leq 1 \times 10^9/L$
Extramedullary disease: Complete resolution of extramedullary disease present before therapy (eg, cutaneous disease, disease-related serous effusions), including palpable hepatosplenomegaly
Provisional category of CR with resolution of symptoms:‡ CR as described above, and complete resolution of disease-related symptoms as noted by the MPN-SAF TSS
Persistent low-level dysplasia is permitted given subjectivity of assignment of dysplasia*
Complete cytogenetic remission
Resolution of previously present chromosomal abnormality (known to be associated with myelodysplastic, syndrome myeloproliferative neoplasms, or MDS/MPN), as seen on classic karyotyping with minimal of 20 metaphases or FISH§
Partial remission
Normalization of peripheral counts and hepatosplenomegaly with bone marrow blasts (and blast

equivalents) reduced by 50%, but remaining >5% of cellularity *except* in cases of MDS/MPN with  $\leq 5\%$  bone marrow blasts at baseline

#### **Marrow response**

Optimal marrow response: Presence of all marrow criteria necessary for CR without normalization of peripheral blood indices as presented above.

Partial marrow response: Bone marrow blasts (and blast equivalents) reduced by 50%, but remaining >5% of cellularity, *or* reduction in grading of reticulin fibrosis from baseline on at least 2 bone marrow evaluations spaced at least 2 mo apart

#### **Clinical benefit**

Requires 1 of the following in the absence of progression or CR/partial response and independent of marrow response (cord blood response must be verified at  $\geq 8$  wk) to be considered a clinical benefit

##### **Erythroid response**

Hgb increase by  $\geq 2.0$  g/dL

TI for  $\geq 8$  wk for patients requiring at least 4 packed red blood cell transfusions in the previous 8 wk

Only red blood cell transfusions given based on physician's judgment for a pretreatment Hgb of  $\leq 8.5$  g/dL will count in the red blood cell TI response evaluation $\perp\!\!\!\perp$

##### **Platelet response**

Transfusion independence when previously requiring platelet transfusions of at least a rate of 4 platelet transfusions in the previous 8 wk

Pretreatment  $\leq 20 \times 10^9/L$ : increase from  $<20 \times 10^9/L$  to  $>20 \times 10^9/L$  and by at least 100%

Pretreatment  $>20 \times 10^9/L$  but  $\leq 100 \times 10^9/L$ : absolute increase of  $\geq 30 \times 10^9/L\perp\!\!\!\perp$

##### **Neutrophil response**

Pretreatment  $\leq 0.5 \times 10^9/L$  at least 100% increase and an absolute increase  $\geq 0.5 \times 10^9/L$

Pretreatment,  $>0.5 \times 10^9/L$  and  $\leq 1.0 \times 10^9/L$  At least 50% increase and an absolute increase  $\geq 0.5 \times 10^9/L\perp\!\!\!\perp$

##### **Spleen response**

Either a minimum 50% reduction in palpable splenomegaly of a spleen that is at least 10 cm at baseline or a spleen that is palpable at more than 5 cm at baseline becomes not palpable

Symptom response

Improvement in symptoms as noted by decrease of  $\geq 50\%$  as per the MPN-SAF TSS scoring <20 were not considered eligible for measuring clinical benefit.¶

- $\underline{d}^*$  Presence of dysplastic changes, which may be interpreted within the scope of normal range of dysplastic changes, may still exist in the presence of CR as allowed in MDS IWG. Marrow should exhibit age-adjusted normocellularity in CR.
- $\underline{d}^{\dagger}$  If there is no significant fibrosis present on the initial bone marrow biopsy, a second biopsy is not required to prove resolution of fibrosis. Grading of fibrosis in measurement of treatment response should be according to the European Consensus System.
- $\underline{d}^{\ddagger}$  Given the current lack of a validated tool to assess complete resolution of symptoms in MDS/MPN, “CR with resolution of symptoms” (a complete resolution of disease-related symptoms as noted by the MPN-SAF TSS in presence of CR) will be a provisional category of disease response.
- $\underline{d}^{\$}$  Loss of cytogenetic burden of disease by (via FISH or classic karyotyping) known to adversely affect prognosis is required to reach complete cytogenetic remission. Decrease in the cytogenetic burden of disease must be by  $\geq 50\%$  (via FISH or classic karyotyping) to be indicative of a partial cytogenetic response. Given variability of fluorescent probes used in FISH, cytogenetic normalization via FISH will depend on the performance characteristics of the specific probes used.

## **12. STUDY OVERSIGHT AND DATA REPORTING / REGULATORY REQUIREMENTS**

Adverse event lists, guidelines, and instructions for AE reporting can be found in Section 7.0 (Adverse Events: List and Reporting Requirements).

### **Data Quality Portal**

The Data Quality Portal (DQP) provides a central location for site staff to manage unanswered queries and form delinquencies, monitor data quality and timeliness, generate reports, and review metrics.

The DQP is located on the CTSU members' website under Data Management. The Rave Home section displays a table providing summary counts of Total Delinquencies and Total Queries. DQP Queries, DQP Delinquent Forms, and the DQP Reports modules are available to access details and reports of unanswered queries, delinquent forms, and timeliness reports. Review the DQP modules on a regular basis to manage specified queries and delinquent forms.

The DQP is accessible by site staff that are rostered to a site and have access to the CTSU website. Staff that have Rave study access can access the Rave study data using a direct link on the DQP.

To learn more about DQP use and access, click on the Help icon displayed on the Rave Home, DQP Queries, and DQP Delinquent Forms modules.

Note: Some Rave protocols may not have delinquent form details or reports specified on the DQP. A protocol must have the Calendar functionality implemented in Rave by the Lead Protocol Organization (LPO) for delinquent form details and reports to be available on the DQP. Site staff should contact the LPO Data Manager for their protocol regarding questions about Rave Calendaring functionality.

### **12.1 Study Oversight**

This protocol is monitored at several levels, as described in this section. The Protocol Principal Investigator is responsible for monitoring the conduct and progress of the clinical trial, including the ongoing review of accrual, patient-specific clinical and laboratory data, and routine and serious adverse events; reporting of expedited adverse events; and accumulation of reported adverse events from other trials testing the same drug(s). The Protocol Principal Investigator and statistician have access to the data at all times through the CTMS web-based reporting portal.

All Study Investigators at participating sites who register/enroll patients on a given protocol are responsible for timely submission of data via Medidata Rave and timely reporting of adverse events for that particular study. This includes timely review of data collected on the electronic CRFs submitted via Medidata Rave.

All studies are also reviewed in accordance with the enrolling institution's data safety monitoring plan.

In addition, the Protocol Principal Investigator will have at least monthly conference calls with the site Study Investigators and study teams to review accrual, progress, adverse events, and unanticipated problems.

## 12.2 Data Reporting

Medidata Rave is a clinical data management system being used for data collection for this trial/study. Access to the trial in Rave is controlled through the CTEP-IAM system and role assignments. To access Rave via iMedidata:

- Site staff will need to be registered with CTEP and have a valid and active CTEP-IAM account, and
- Assigned one of the following Rave roles on the relevant Lead Protocol Organization (LPO) or Participating Organization roster at the enrolling site: Rave CRA, Rave Read Only, Rave CRA (LabAdmin), Rave SLA, or Rave Investigator. Refer to <https://ctep.cancer.gov/investigatorResources/default.htm> for registration types and documentation required.
  - To hold Rave CRA or Rave CRA (Lab Admin) role, site staff must hold a minimum of an AP registration type,
  - To hold Rave Investigator role, the individual must be registered as an NPIVR or IVR, and
  - To hold Rave Read Only role, site staff must hold an Associates (A) registration type.

Upon initial site registration approval for the study in Regulatory Support System (RSS), all persons with Rave roles assigned on the appropriate roster will be sent a study invitation e-mail from iMedidata. To accept the invitation, site staff must log in to the Select Login (<https://login.imedidata.com/selectlogin>) using their CTEP-IAM username and password, and click on the accept link in the upper right-corner of the iMedidata page. Site staff will not be able to access the study in Rave until all required Medidata and study specific trainings are completed. Trainings will be in the form of electronic learnings (eLearnings), and can be accessed by clicking on the link in the upper right pane of the iMedidata screen. If an eLearning is required and has not yet been taken, the link to the eLearning will appear under the study name in iMedidata instead of the Rave EDC link; once the successful completion of the eLearning has been recorded, access to the study in Rave will be granted, and a Rave EDC link will display under the study name.

Site staff that have not previously activated their iMedidata/Rave account at the time of initial site registration approval for the study in RSS will also receive a separate invitation from iMedidata to activate their account. Account activation instructions are located on the CTSU website in the Rave section under the Rave resource materials (Medidata Account Activation and Study Invitation Acceptance).

Additional information on iMedidata/Rave is available on the CTSU members' website in the Data Management > Rave section at [www.ctsu.org/RAVE/](http://www.ctsu.org/RAVE/) or by contacting the CTSU Help Desk at [name] or by e-mail at [[contact]](mailto:[contact]).

#### 12.2.1 Method

This study will be monitored by the Clinical Trials Monitoring Service (CTMS). Data will be submitted to CTMS at least once every two weeks via Medidata Rave (or other modality if approved by CTEP). Information on CTMS reporting is available at <http://www.theradex.com/clinicalTechnologies/?National-Cancer-Institute-NCI-11>. On-site audits will be conducted three times annually (one annual site visit and two data audits). For CTMS monitored studies, after users have activated their accounts, please contact the Theradex Help Desk at [contact] or by email at [[contact]](mailto:[contact]) for additional support with Rave and completion of CRFs.

#### 12.2.2 Responsibility for Data Submission

For ETCTN trials, it is the responsibility of the PI(s) at the site to ensure that all investigators at the ETCTN Sites understand the procedures for data submission for each ETCTN protocol and that protocol specified data are submitted accurately and in a timely manner to the CTMS via the electronic data capture system, Medidata Rave.

Data are to be submitted via Medidata Rave to CTMS on a real-time basis, but no less than once every 2 weeks. The timeliness of data submissions and timeliness in resolving data queries will be tracked by CTMS. Metrics for timeliness will be followed and assessed on a quarterly basis. For the purpose of Institutional Performance Monitoring, data will be considered delinquent if it is greater than 4 weeks past due.

Data from Medidata Rave and CTEP-AERS is reviewed by the CTMS on an ongoing basis as data is received. Queries will be issued by CTMS directly within Rave. The queries will appear on the Task Summary Tab within Rave for the CRA at the ETCTN to resolve. Monthly web-based reports are posted for review by the Drug Monitors in the IDB, CTEP. Onsite audits will be conducted by the CTMS to ensure compliance with regulatory requirements, GCP, and NCI policies and procedures with the overarching goal of ensuring the integrity of data generated from NCI-sponsored clinical trials, as described in the ETCTN Program Guidelines, which may be found on the CTEP ([http://ctep.cancer.gov/protocolDevelopment/electronic\\_applications/adverse\\_events.htm](http://ctep.cancer.gov/protocolDevelopment/electronic_applications/adverse_events.htm)) and CTSU websites.

An End of Study CRF is to be completed by the PI, and is to include a summary of study endpoints not otherwise captured in the database, such as (for phase 1 trials) the recommended phase 2 dose (RP2D) and a description of any dose-limiting toxicities (DLTs). CTMS will utilize a core set of eCRFs that are Cancer Data Standards Registry and Repository (caDSR) compliant (<http://cbiit.nci.nih.gov/ncip/biomedical-informatics-resources/interoperability-and-semantics/metadata-and-models>). Customized eCRFs will be included when appropriate to meet unique study requirements. The PI is encouraged to

review the eCRFs, working closely with CTMS to ensure prospectively that all required items are appropriately captured in the eCRFs prior to study activation. CTMS will prepare the eCRFs with built-in edit checks to the extent possible to promote data integrity.

CDUS data submissions for ETCTN trials activated after March 1, 2014, will be carried out by the CTMS contractor, Theradex. CDUS submissions are performed by Theradex on a monthly basis. The trial's lead institution is responsible for timely submission to CTMS via Rave, as above.

Further information on data submission procedures can be found in the ETCTN Program Guidelines ([http://ctep.cancer.gov/protocolDevelopment/electronic\\_applications/adverse\\_events.htm](http://ctep.cancer.gov/protocolDevelopment/electronic_applications/adverse_events.htm)).

### **12.3 CTEP Multicenter Guidelines**

N/A

### **12.4 Collaborative Agreements Language**

The agent(s) supplied by CTEP, DCTD, NCI used in this protocol is/are provided to the NCI under a Collaborative Agreement (CRADA, CTA, CSA) between the Pharmaceutical Company(ies) (hereinafter referred to as "Collaborator(s)") and the NCI Division of Cancer Treatment and Diagnosis. Therefore, the following obligations/guidelines, in addition to the provisions in the "Intellectual Property Option to Collaborator" ([http://ctep.cancer.gov/industryCollaborations2/intellectual\\_property.htm](http://ctep.cancer.gov/industryCollaborations2/intellectual_property.htm)) contained within the terms of award, apply to the use of the Agent(s) in this study:

1. Agent(s) may not be used for any purpose outside the scope of this protocol, nor can Agent(s) be transferred or licensed to any party not participating in the clinical study. Collaborator(s) data for Agent(s) are confidential and proprietary to Collaborator(s) and shall be maintained as such by the investigators. The protocol documents for studies utilizing Agents contain confidential information and should not be shared or distributed without the permission of the NCI. If a copy of this protocol is requested by a patient or patient's family member participating on the study, the individual should sign a confidentiality agreement. A suitable model agreement can be downloaded from: <http://ctep.cancer.gov>.
2. For a clinical protocol where there is an investigational Agent used in combination with (an)other Agent(s), each the subject of different Collaborative Agreements, the access to and use of data by each Collaborator shall be as follows (data pertaining to such combination use shall hereinafter be referred to as "Multi-Party Data"):
  - a. NCI will provide all Collaborators with prior written notice regarding the existence and nature of any agreements governing their collaboration with NCI, the design of the proposed combination protocol, and the existence of any obligations that would tend to

restrict NCI's participation in the proposed combination protocol.

- b. Each Collaborator shall agree to permit use of the Multi-Party Data from the clinical trial by any other Collaborator solely to the extent necessary to allow said other Collaborator to develop, obtain regulatory approval or commercialize its own Agent.
  - c. Any Collaborator having the right to use the Multi-Party Data from these trials must agree in writing prior to the commencement of the trials that it will use the Multi-Party Data solely for development, regulatory approval, and commercialization of its own Agent.
3. Clinical Trial Data and Results and Raw Data developed under a Collaborative Agreement will be made available to Collaborator(s), the NCI, and the FDA, as appropriate and unless additional disclosure is required by law or court order as described in the IP Option to Collaborator ([http://ctep.cancer.gov/industryCollaborations2/intellectual\\_property.htm](http://ctep.cancer.gov/industryCollaborations2/intellectual_property.htm)). Additionally, all Clinical Data and Results and Raw Data will be collected, used and disclosed consistent with all applicable federal statutes and regulations for the protection of human subjects, including, if applicable, the *Standards for Privacy of Individually Identifiable Health Information* set forth in 45 C.F.R. Part 164.
4. When a Collaborator wishes to initiate a data request, the request should first be sent to the NCI, who will then notify the appropriate investigators (Group Chair for Cooperative Group studies, or PI for other studies) of Collaborator's wish to contact them.
5. Any data provided to Collaborator(s) for Phase 3 studies must be in accordance with the guidelines and policies of the responsible Data Monitoring Committee (DMC), if there is a DMC for this clinical trial.
6. Any manuscripts reporting the results of this clinical trial must be provided to CTEP by the Group office for Cooperative Group studies or by the principal investigator for non-Cooperative Group studies for immediate delivery to Collaborator(s) for advisory review and comment prior to submission for publication. Collaborator(s) will have 30 days from the date of receipt for review. Collaborator shall have the right to request that publication be delayed for up to an additional 30 days in order to ensure that Collaborator's confidential and proprietary data, in addition to Collaborator(s)'s intellectual property rights, are protected. Copies of abstracts must be provided to CTEP for forwarding to Collaborator(s) for courtesy review as soon as possible and preferably at least three (3) days prior to submission, but in any case, prior to presentation at the meeting or publication in the proceedings. Press releases and other media presentations must also be forwarded to CTEP prior to release. Copies of any manuscript, abstract and/or press release/ media presentation should be sent to:

Email: [[contact]](mailto:[contact])

The Regulatory Affairs Branch will then distribute them to Collaborator(s).

No publication, manuscript or other form of public disclosure shall contain any of Collaborator's confidential/ proprietary information.

## **12.5 Genomic Data Sharing Plan**

Genomic data obtained as part of this study will be shared according to the data sharing plan of the NCI. Please refer to the NCI Genomic Data Sharing Policy at <http://www.cancer.gov/grants-training/grants-management/nci-policies/genomic-data> for considerations regarding the sharing of data, protection of patient confidential information, and the provision of adequate information in the patient informed consent.

## 13. STATISTICAL CONSIDERATIONS

### 13.1 Study Design/Endpoints

This phase II study will randomize patients 2:1 to Arm A (T/C/V) or to the standard Arm B (T/C), respectively. The primary end point is Overall Response (CR/CRi). We expect that these MPN patients will fall into two risk categories based on the percent blasts at baseline: < 20% blasts versus 20% or higher. The expected CR/CRi rate with traditional regimens in this group of patients ranges from 14% for patients with worse disease to 29% for patients with blasts 20% or higher.

For each group, the level of response that would confer interest in pursuing the therapy is a CR/CRi rate of 58%. This CR/CRi response rate was the response rate seen in our phase I trial in the subset of MPN patients with a lower response rate (those with less than 20% blasts), where we observed responses in 7 out of 12 cases (58.3%). The proportion of patients in each subgroup are assumed to be 33% in the low blast count group and 67% in the higher blast count group, respectively. These proportions are considered in the sample size calculation. The final analysis will be by an exact Cochrane-Mantel-Haenszel test, which tests for an overall treatment difference while adjusting for subgroup. The primary analysis will conclude a significant benefit for Arm A over Arm B if the one-sided p value < 0.10.

The study design includes interim monitoring for futility (i.e., stopping early if there is high probability that the study will not show a significant benefit for Arm A over Arm B). Futility is based on the predictive probability of a statistically significant treatment difference at the end of the study if the study enters, treats, and follows the total number of patients planned for the study. If we determine at any interim analysis that there is a < 10% chance of ultimately finding a statistically significant difference between Arm A and Arm B, we will pause for a safety review by the PI, study team, and CTEP if one of the stopping boundaries is hit. We determined the predictive probability of a significant trial result through simulations using a beta-binomial model to predict future observations conditional on data available at the time of the test. In the simulations, the predicted test was an exact Cochran-Mantel-Haenszel test, and a predicted test was significant if the one-sided p value of the test was < 0.10, as stated in the primary analysis.

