### 2.3 Topotecan & Carboplatin

Topotecan and carboplatin induce synergistic cytotoxicity in acute leukemia cell lines and primary AML cells *in vitro*. This observation was the basis for a phase I study of topotecan + carboplatin by five-day intravenous continuous infusion (IV CI) in adults with relapsed or refractory acute leukemia. Oral and gastrointestinal (GI) mucositis were the dose limiting toxicities (DLTs) of this combination. Complete remissions (CRs) were observed at multiple dose levels, including 3 of 6 patients at the maximum tolerated dose (MTD) of topotecan 1.6 mg/m^2/day and carboplatin 150 mg/m^2/day simultaneously for 5 days. A subsequent ECOG Phase II trial of topotecan/carboplatin at this MTD resulted in CRs in 5 of 35 (14%) patients with relapsed and refractory AML, a response rate similar to a mitoxantrone/etoposide/cytarabine- (MEC-) based arm in the same trial. This Phase II trial of topotecan and carboplatin only studied the doses of 1.6 mg/m^2/day topotecan with 150 mg/m^2/day of carboplatin combination. In the phase I study of the combination, there were 21 evaluable patients in the doses below the 1.2 mg/m^2/150 mg/m^2 combination and responses in 3 of these patients (14%). In the dose levels above 1.2/150, there were 14 patients treated with 6 responses (43%). These data should be interpreted with caution, however, as these patients included a mixture of acute myeloid leukemia, acute lymphoid leukemia, myelodysplastic syndrome, and blast crisis CML. Of the 46 patients on this phase I study, only three had antecedent myeloproliferative disorders, which is the study population we are targeting with the present study. In the control ARM B we will use the recommended phase II dose of topotecan (1.6mg/m^2/day) in combination with carboplatin to maximize chemotherapeutic exposure in absence of veliparib.

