### 3. PATIENT SELECTION

#### 3.1 Pre-Registration Eligibility Criteria

3.1.1 Patient has or suspected to have one of the following:

- Newly diagnosed Acute Myeloid Leukemia (AML) associated with antecedent myeloproliferative disorder (Polycythermia Vera, Essential Thrombocythemia, Myelofibrosis, atypical Chronic Myeloid Leukemia, Chronic Myelomonocytic Leukemia and related undifferentiated myeloproliferative/myelodysplastic disorders)
- Relapsed/refractory AML associated with antecedent myeloproliferative disorder (Polycythermia Vera, Essential Thrombocythemia, Myelofibrosis, atypical Chronic Myeloid Leukemia , Chronic Myelomonocytic Leukemia and related undifferentiated myeloproliferative/myelodysplastic disorders) who have received two or fewer prior induction chemotherapy courses
- Accelerated phase myeloproliferative disorders per Zeider et al with two or fewer prior therapies.
  - For aggressive phase MPD (P. Vera, essential thrombocythemia, Ph-negative chronic myelogenous leukemia), one or more of the following criteria must be met: marrow blasts >5%, peripheral blood blasts plus progranulocytes > 10%, new onset or increasing myelofibrosis, new onset or > 25% increase in hepatomegaly or splenomegaly, new onset constitutional symptoms (fever, weight loss, spleni pain, bone pain). Zeider et al
  - For Chronic Myelomonocytic Leukemia (CMML), the following criteria must be met: 5-19% bone marrow blasts (aggressive) or  $\geq$  20% marrow blasts (transformation).

3.1.2 Bone marrow and/or peripheral blood specimens will be submitted for correlative studies as outlined in Section 9. Patients with a dry tap will still be eligible.

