### 13.2 Sample Size/Accrual Rate

We expect to enroll 1-2 patients per month at JHU alone. With 7-8 other centers participating in this study, we expect their accrual to average 3 patients per month, for a study-wide total of 3 patients per month. We fully expect that we will be able to complete accrual in 12-16 months, allowing for some patients who may drop out before randomization, and accrual holds for interim analysis.

The futility analysis will begin when 24 patients (16 in Arm A, 8 in Arm B) have entered the study and received treatment. If the study does not stop after the first interim analysis, a second interim analysis will be done when another 18 (12 in Arm A, 6 in Arm B) patients have entered the study and received treatment (42 patients total). Each interim analysis will project the remaining patients yet to be enrolled and compute the predicted significance level of the primary analysis, conditional on the data available at the time of analysis (i.e., predictive power).

The prior distribution for the interim futility analyses is a non-informative beta(1,1) prior. Provided the study does not stop for futility, the final sample size will be 60 patients, with 40 in Arm A and 20 in Arm B.

The operating characteristics of the design are shown in the table below. We performed 1,000 simulations with varying values of the underlying probability of a response for each treatment and disease subgroup. The table shows that this study will have approximately 91% power to detect an increase (given in the first paragraph of this section) in the subgroup-specific probabilities of a complete response for Arm A compared to Arm B.

Sample Size (A / B)	Probability of a CR in < 20% blasts group (A / B)	Probability of a CR in 20% or higher blasts group (A / B)	Estimated Power	Probability of stopping early at each interim analysis (1st / 2nd)	Cumulative probability of stopping early	Probability of failing to reject at the end of the study
40 / 20	0.58 / 0.29	0.58 / 0.14	0.91	0.042 / 0.014	0.056	0.034
	0.40 / 0.29	0.40 / 0.14	0.475	0.182 / 0.125	0.307	0.218
	0.29 / 0.29	0.14 / 0.14	0.036	0.638 / 0.214	0.852	0.112

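### Sections 13.1 and 13.2 assign the 29% and 14% control response rates to opposite blast groups; the stated 91% power fits the table, while the text's rates give about 82%

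*Combined protocol and SAP*

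**What the plan says.** Section 13.1 defines two risk groups by baseline blasts, below 20% and 20% or higher. It says the CR/CRi rate on traditional regimens "ranges from 14% for patients with worse disease to 29% for patients with blasts 20% or higher". The target for Arm A is 58% in both groups. The mix is "assumed to be 33% in the low blast count group and 67% in the higher blast count group", and 13.1 says these proportions enter the sample size calculation.

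The table in Section 13.2 has one column for the group below 20% and another headed "Probability of a CR in 20% or higher blasts group (A / B"). In all three rows the Arm B rate is 0.29 in the first column and 0.14 in the second. The first row (0.58/0.29 and 0.58/0.14) carries an estimated power of 0.91. The text above the table says "this study will have approximately 91% power to detect an increase (given in the first paragraph of this section").

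**The concern.** The two sections give the control rates to opposite groups. With only two groups defined, giving 29% to the higher-blast group leaves 14% for the lower one, and the table has them the other way round. The cross-reference attached to the 91% does not help. The first paragraph of 13.2 is about accrual, and the only opening paragraph in Section 13 that states control rates is the one in 13.1, which has the contrary assignment.

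Blast group is both the randomisation stratum and the adjustment factor in the primary test, and the groups are assumed unequal in size. The assignment therefore decides whether two thirds of patients have the larger planned difference (58% against 14%) or the smaller one (58% against 29%). At stake are the stated power and the stated chance of stopping for futility when the planned effect is real.

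**Working it through.** **Inputs.** From 13.1: one-sided exact Cochran-Mantel-Haenszel test at p < 0.10, Arm A rate 0.58 in both groups, mix 33/67, and a futility stop when the predictive probability of a significant result is below 10%. From 13.2: 40 patients in Arm A and 20 in Arm B, looks at 24 patients (16/8) and 42 patients (28/14), and a beta(1,1) prior.

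**Assumed, because the plan does not state it.** Stratum sizes are the 33/67 mix rounded within each arm (below 20% / 20% or higher):
- final: A 13/27, B 7/13
- first look: A 5/11, B 3/5
- second look: A 9/19, B 5/9

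Each arm-by-stratum cell has its own beta(1,1) prior, and crossing the futility boundary counts as stopping.

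**Formulas.**
- Final test: let T be the number of Arm A responders summed over the two strata. Given the total responders in each stratum, T under the null is the sum of two independent hypergeometric variables. Reject if P(T ≥ observed) < 0.10.
- Predictive probability: with x responders among n patients in a cell, future responders are beta-binomial with parameters 1 + x and 1 + n − x. Stop if the predictive probability of rejection is below 0.10.
- Power is the probability of passing both looks and then rejecting, computed by exact recursion over the four cells.

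**Plan's own figures first, then the text's rates.**

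| Quantity | Plan | Table's rates | Text's rates |
|---|---|---|---|
| Power, 58% target | 0.91 | 0.908 | 0.819 |
| Stop at 1st / 2nd look | 0.042 / 0.014 | 0.035 / 0.019 | 0.071 / 0.036 |
| Any early stop | 0.056 | 0.054 | 0.107 |
| Power, 40% row | 0.475 | 0.496 | 0.334 |
| Rejection under the null | 0.036 | 0.043 | 0.046 |

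Over 64 ways of rounding the stratum sizes, power runs from 0.905 to 0.918 on the table's rates and from 0.805 to 0.822 on the text's. Separate simulations agree: 0.912 with fixed and 0.902 with random stratum sizes on the table's rates, against 0.819 and 0.820 on the text's.

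**Simulation noise does not explain the gap.** The plan used 1,000 simulations. The standard error at 0.91 is √(0.91 × 0.09 / 1000) = 0.009, and the gap from 0.91 to 0.819 is about ten times that. At 0.475 it is √(0.475 × 0.525 / 1000) = 0.016. The plan's value lies about 1.3 standard errors from 0.496 and about 9 from 0.334.

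**Why power moves.** The mean control rate is 0.33 × 0.29 + 0.67 × 0.14 = 0.190 on the table's rates and 0.33 × 0.14 + 0.67 × 0.29 = 0.241 on the text's. The mean difference from 0.58 falls from 0.39 to 0.34.

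**Dependence on the mix.** At 50/50 (A 20/20, B 10/10) power is 0.868 under either assignment. At 67/33 the results swap: 0.908 for the text's rates and 0.819 for the table's. The text's rates reach 91% only if the stated mix is reversed as well.

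**The case against.** The strongest reply is that this is a wording slip with a visible answer. All three rows agree with each other, and the plan's power and stopping figures reproduce on the table's rates and not on the swapped ones, so what was simulated is known. Other parts of the plan fit the table. The 14% is attached to worse disease. Section 3.1 describes CMML with "5-19% bone marrow blasts (aggressive") as the less advanced state and 20% or more as transformation. Section 2.3 reports that topotecan/carboplatin at the Arm B dose "resulted in CRs in 5 of 35 (14%) patients with relapsed and refractory AML". All this makes the table the likelier intention. It does not settle the matter, because 13.1 does not cite that trial, or any other source, for its 14% or 29%. Section 13.1 also calls the group below 20% blasts the phase I subset with the lower response rate. That is weak evidence about control rates, since those patients received veliparib.

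Three narrower points also have force:
- 13.1 never states 14% for blasts below 20%. It follows by elimination from a sentence that contrasts severity with a blast category.
- The cross-reference is loose: the first paragraph of 13.1 gives only control rates, and the 58% target is in the second.
- The 82% counts every futility crossing as a stop, whereas 13.1 describes a pause for review. Without futility stops, exact power is 0.856 on the text's rates and 0.932 on the table's.

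The last point softens the loss but leaves a gap of about eight points. The 82% is the figure comparable with the plan's 91%, whose table reports early stopping. None of these points removes the contradiction.

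**Conclusion.** The concern holds. The two sections contradict each other on the control rates behind the primary power statement. The 91% belongs to the table's assignment at the 33/67 mix. On the text's assignment, power is about 82%, the chance of missing the planned effect about 18% instead of 9%, and the chance of an unwarranted futility stop about 11% instead of 5%. These figures assume rounded 33/67 strata, cell-wise beta(1,1) priors and futility crossings treated as stops.

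This does not show that the trial is underpowered. The evidence favours the table, and in that case 91% stands. The rejection rate under the null is nearly the same either way (0.043 and 0.046). It should be fixed because the plan's stated justification and its calculation disagree on a primary planning assumption, and only the authors can confirm which is meant.

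**What to change.** State in both 13.1 and 13.2 which blast group carries 29% and which 14%, give the source of each rate, and confirm the 33/67 mix at the same time, because power depends on the two together. Point the cross-reference in 13.2 to the paragraphs of 13.1 that hold the control rates and the target.

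- **If the table and the mix are right:** correct the 13.1 sentence to 29% for blasts below 20% and 14% for blasts of 20% or higher. The 91% stands and nothing needs rerunning.
- **If the text is right:** rerun the existing simulation with the control rates exchanged, replace all three rows of the table, and restate power as about 82% for the same 60 patients.

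The likely cost is one corrected phrase; otherwise it is a rerun of existing code and a less favourable power statement. Neither route requires a change to the sample size, the test, the randomisation or the futility rule.
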